6 HANDLING OF MISSING DATA AND OTHER DATA CONVENTIONS

Missingness will be evaluated using standard procedures when analyzing repeated measures data (van Buuren, 2018). First, missingness codes will be created that correspond with the variables in which data points are missing. A series of variables will be created that indicate missingness in each outcome at each measurement time point. We will then explore the extent to which various demographic markers and other variables in the dataset associate with missingness through a series of correlation tests. This practice will ultimately help us determine auxiliary variables for our models.

When working with missing data, there are two “gold standard” approaches to mitigating bias: multiple imputation and full information maximum likelihood (ML) estimation. However, as will be detailed below, multilevel modeling benefits from the fact that the approach does not assume that each group or cluster is balanced. In other words, even if individual A only has a baseline, but individual B has all four observations, no assumptions are violated, and the model will be unbiased (Raudenbush & Bryk, 2002). Thus, multilevel modeling allows us to avoid using a traditional missing data approach by simply harnessing the model’s extant capabilities. Given that we do not anticipate any significant missing data in the predictors or covariates, we plan to use restricted maximum likelihood (REML) estimation in the multilevel framework to account for missing outcome variable data. Final models will be run with identified auxiliary variables included as covariates.

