required to pass at least one of the attention checks in the baseline assessment. These attention checks require people to select a specific response option (e.g., for the PSS, an attention check item could instruct the participant to select “Never”, and this would vary across all assessments). Participants who complete and pass the baseline assessment on Qualtrics will be randomly assigned, via a Qualtrics randomization tool, to either the experimental or waitlist control group, and will receive an email or text (through Simple Text) with information detailing their condition on their corresponding start date. If they are in the experimental condition, they will also receive a link to download Happify. Both groups will complete assessments at 4 (mid-point), 8 (immediate post-intervention), and 12 weeks (one month post-intervention) via their preferred method of contact which was obtained in the baseline (e.g. email or text). All participants will be prompted to provide their user ID and complete the PSS, RRS - Brooding Subscale, LOT-R, PROMIS Pediatric Sleep Disturbance scale, and the RULS-8 via Qualtrics at each assessment point. Participants will also be asked at each assessment point if they have sought out help from other online platforms and what their current schooling situation is (fully remote, hybrid model, fully in person, home-schooled, or not in school). All of the assessments will have one attention check per questionnaire, which will instruct participants to select a specific response option to ensure they are reading questionnaire items and instructions carefully. The SLSS and PANAS-C-S will be administered only during baseline for scale validation purposes, and the experimental group will receive the Happify scale as part of the app experience every 2 weeks. In both cases, participants who do not qualify for the study will be thanked and alerted through Qualtrics that they do not qualify, and all their survey information will be deleted to protect their confidentiality. Participants who do not complete the baseline assessment will not go onto the study and will also have all of their information deleted.

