  - b. Gender Question (optional): Participants will be asked “What is your gender?” and they will be provided with a text box to type in their response.
  - c. Age: “What year were you born?” (text box to respond)
  - d. Parental Happify Usage: “To your knowledge, have either of your parents used Happify before?”; participants will

respond with “Not that I know of”, “Yes, one of my parents” or “Yes, both of my parents”

5. Schooling Question (at each assessment point): 1 item asking “What is your schooling situation right now?” Participants will select from “Fully in person”, “Fully online learning”, “Hybrid model”, “Homeschool”, or “Do not attend school.”
6. Self-Care App Use (at each assessment point): 1 item asking participants if they have used any self-care or wellness apps. If they indicate yes, they will be prompted with “Which apps?” in which they will type in their response.

iv. Participants will receive reminders if they have not completed these assessments on time, and if a participant has not completed an assessment within 7 days of its scheduled date, a member of the research team will reach out via text message or email (depending on their preferred mode of contact) to check in. We will remind them that they receive \$20 for every major assessment completed (after baseline) and receive a \$20 bonus for completing all four assessments.

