#### **e. Design and Proposed Statistical Analysis**

**I. Changes in Stress and Secondary/Exploratory Outcomes:** To assess whether changes in participants' perceived stress differed across the two groups, we plan to conduct a 2 (group: intervention vs. control) x 4 (time: baseline, 4 weeks, 8 weeks, 12 weeks) repeated-measures ANOVA on participants' PSS scores, controlling for participant age and gender. Similar analyses will be conducted on secondary and exploratory outcome measures. To determine whether usage predicted changes in these outcomes, we will also conduct regression analyses among participants in the intervention condition regressing their scores on each outcome variable onto the number of activities completed within the Happify for Teens platform, while controlling for corresponding baseline scores on that outcome.

ii. **Rumination as a Potential Mediator:** To test whether any observed changes in perceived stress can be attributed to changes in brooding, we also plan to conduct mediation analyses using Hayes' PROCESS macro for SPSS.

iii. **Data Exclusion:** Because careless responding is problematic with online surveys and may artificially increase relationships between variables, we plan to use two separate a priori mechanisms for identifying low quality data: (1) failing 3 or more attention checks in an assessment, and (2) completing an assessment at a rate faster than 1 second per item. We will then re-run the analyses described above without these participants to test whether effects differ when removing low quality data.

iv. **Happify Scale Validation:** To validate the scale for internal purposes, we will conduct confirmatory factor analysis testing the two-factor structure of the scale, and examine convergent validity by computing correlations between the positive emotion subscale and the PANAS-C-S and between the life satisfaction subscale and the SLSS that are collected at baseline.

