### III. RECRUITMENT

a. **Study Population:** This study will recruit adolescents aged 13-17 (Target  $N=800$ ) by advertising to parents on social media (e.g. Facebook, online forums, word of mouth etc...) and existing Happify users who have previously indicated they are parents of adolescents as part of the Happify onboarding process. We will also use a snowballing recruitment method, in which parents who complete the prescreener will be encouraged to share the study with others. We will continue recruiting until 800 participants have met inclusion criteria, successfully completed the baseline assessment, and have started the study.

b. **Inclusion Criteria:** Participants are those who are 13-17 years old, are located in the United States, are a new user of Happify, willing and able to complete the study activities, agree to potentially being selected for the waitlist comparison, agree to not discuss the study with friends or family, report elevated levels of perceived stress (PSS score of at least 14) and rumination (RRS-Brooding score of at least 10), and have a

parent who is willing to consent to the study. Participants are required to complete and pass the baseline assessment to be included in this study.

**c. Exclusion Criteria:** Participants may withdraw from the study or skip assessments at any time; however during the prescreening and/or baseline process, potential participants will be disqualified if they indicate:

- i. They are not 13-17 years old.
- ii. They reside outside of the United States
- iii. They have previously registered for or used Happify
- iv. They are not willing and able to complete the study activities
- v. They indicate that they are not willing to continue the study or refrain from downloading Happify if selected to be on the waitlist
- vi. They are not willing to use a mobile app or internet website
- vii. They do not agree to refraining from discussing the study with friends or family
- viii. They have a PSS score of below 14
- ix. They have an RRS-Brooding score of less than 10
- x. They do not agree to be contacted
- xi. Their parent does not consent to the study
- xii. Participants will also be excluded if they do not complete the baseline assessment, or if they do but fail at least 7/7 attention checks.

2. **Sample Size:** We will recruit 800 participants to be in this study, 400 in each condition.

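### SAP 6 calls the multilevel model unbiased under unequal follow-up without stating a missing-at-random condition, plans no sensitivity analysis for dropout, and does not restrict auxiliary covariates to pre-randomisation variables

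*SAP*

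**What the plan says.** SAP 6 sets out three steps. First, it codes missingness in each outcome at each visit and tests how far "various demographic markers and other variables in the dataset associate with missingness through a series of correlation tests". Second, it names multiple imputation and full-information maximum likelihood as the two leading approaches, then argues that a multilevel model needs neither because it does not require balanced clusters. Its example is one participant with only a baseline and another with all four observations, for whom "no assumptions are violated, and the model will be unbiased". Third, it gives the resulting plan: "Given that we do not anticipate any significant missing data in the predictors or covariates", REML will deal with missing outcomes, and "Final models will be run with identified auxiliary variables included as covariates".

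SAP 5 lists age, gender and race as covariates for every model but does not say that nothing else may be added. The assumption checks in SAP 7.2 cover residual linearity, normality and homogeneity, and correlation between random and fixed effects; missingness is not among them. The planned re-runs are the attention-check exclusion (SAP 7.1; Protocol II.e) and, in the protocol only, exclusion for "completing an assessment at a rate faster than 1 second per item".

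**The concern.** The reason given in SAP 6 is about design: the model can be fitted when people have different numbers of visits. The conclusion is about bias, and it does not follow. REML is a likelihood method. With incomplete outcomes its estimates can be trusted if missingness depends only on what the model conditions on, and if that model is right. If teenagers in the Happify arm whose stress is worse than their earlier scores suggest are the ones who stop responding, the available-data comparison flatters the intervention, and no planned analysis shows by how much. The sentence matters because the SAP relies on it to set aside any other missing-data method.

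The auxiliary rule raises a second problem. It selects variables by their correlation with missingness and puts them into the outcome model as fixed covariates, whenever they were measured. A variable measured after randomisation may itself respond to treatment, and conditioning on it changes what the Condition coefficient means.

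**Working it through.** **What the documents supply.** There is no dropout rate, PSS standard deviation or correlation, so there is no figure of the plan's own to reproduce. The usable inputs are the SAP 7.2 equation (Condition and Time as fixed effects, starting with a random intercept) and Protocol III: "We will recruit 800 participants to be in this study, 400 in each condition". Everything else below is assumed.

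**Does the missingness mechanism matter when the model form is right?** A simulation used arm-by-visit terms, SD 6 points, within-person correlation 0.5, a true week-8 difference of −1.5 points, and about 23% to 27% missing at week 8 in each arm. The REML estimates (Monte Carlo error 0.02) were:
- −1.49 with dropout completely at random;
- −1.53 with Happify-arm dropout depending on the previous observed score;
- −1.74 to −2.36 with Happify-arm dropout depending on the current unseen score, from weak to strong dependence.

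So REML held up under missing at random and failed otherwise, although the missing shares in the two arms were similar. Similar dropout rates would therefore not reveal the problem.

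**Size on the written equation.** Work in SD units with PSS SD 1, within-person correlation 0.5, a random intercept, and monotone dropout at the same rates in both arms. Take arm differences of 0/−0.15/−0.30/−0.30 at baseline and weeks 4, 8 and 12 (negative favours Happify).

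1. On completed data the Condition term is the plain mean of the four arm differences: (0 − 0.15 − 0.30 − 0.30)/4 = −0.1875.
2. Let a share m of Happify scores be missing at each week, and let each be worse than predicted by delta. Adding delta to the imputed scores shifts the term by delta × (m4 + m8 + m12)/4. The multipliers are (0.1 + 0.2 + 0.3)/4 = 0.150, (0.2 + 0.3 + 0.4)/4 = 0.225 and (0.3 + 0.4 + 0.5)/4 = 0.300. The shift therefore runs from 0.25 × 0.150 = 0.0375 to 0.5 × 0.300 = 0.15 SD.
3. That shift is the distance between two imputed analyses. For the planned estimate, compare the expected available-data term (generalised least squares on the written equation) with the adjusted value, −0.1875 + shift:

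| Missing at weeks 4/8/12 | Planned term | Adjusted, delta 0.25 | Gap | Adjusted, delta 0.5 | Gap |
|---|---|---|---|---|---|
| 10/20/30% | −0.161 | −0.150 | 0.011 | −0.1125 | 0.049 |
| 20/30/40% | −0.147 | −0.131 | 0.016 | −0.075 | 0.072 |
| 30/40/50% | −0.132 | −0.1125 | 0.019 | −0.0375 | 0.094 |

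The sampling SD of the planned term at 400 per arm is 0.058 to 0.060, so the gap is about 0.2 (0.011/0.058) to 1.6 (0.094/0.060) sampling SDs. In every cell the planned term is the more favourable to Happify. The planned terms differ from −0.1875 because the equation gives Condition one constant effect; that is a separate matter, and it is why the gap is smaller than the shift.

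**Auxiliary covariates.** Suppose treatment moves an auxiliary by a, and the auxiliary has coefficient b in the PSS model given arm. The Condition term then moves from τ to τ − a × b. Nothing is lost if a = 0, which randomisation ensures in expectation for anything measured beforehand. Which variables could the section 6 rule select?
- Same-visit brooding: hardly. Protocol II.a collects it in the same questionnaire as PSS, so a missed assessment loses both and the correlation with missingness cannot be formed.
- App usage: SAP 2 pulls it for the Happify arm only, so there is no waitlist value to enter in a two-arm model.
- An earlier-visit score, such as week-4 brooding correlated with missing week-8 PSS: yes. SAP 3 treats brooding as a possible mediator, so a non-zero a is plausible.

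**The case against.** The strongest reply is that section 6 is missing-at-random practice in all but name. It codes missingness by visit, looks for its correlates, adds them, and fits a likelihood-based model. That stands: neither the choice of REML nor the search for correlates is at fault. What is missing is the stated condition and any check on departures from it.

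A second reply is that the covariate point rests on what the SAP fails to forbid. This is largely fair. A reader might infer that the SAP plans to adjust the treatment comparison for app usage or post-baseline brooding. The documents do not support that: neither is named as an auxiliary, SAP 7.3 models both separately, and section 6 expects little missing covariate data, which an earlier-visit score would not satisfy. The rule still admits such a score, and one clause closes the gap. For an auxiliary with one value per person, the damage falls on the Condition term that SAP 7.2 prints; a Condition-by-Time contrast would be unaffected.

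Third, SAP 7.2's remark about attrition can be read as a general statement on repeated-measures data. It is not used here as a rate for this trial.

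**Conclusion.** The concern holds as a fault of wording and of a missing sensitivity analysis. The unbiasedness claim needs a condition that neither document gives, no planned analysis addresses dropout, and the auxiliary rule has no timing limit.

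The size is illustrative only. Under the assumptions listed, the planned Condition term differs from the delta-adjusted value by about 0.01 to 0.09 SD. A reader might take the 0.04 to 0.15 SD shift as the bias of the planned estimate; it is not, because it compares two imputed analyses. Nor do the documents show that the trial's result will be biased. If outcomes are missing at random in a correctly specified model and only pre-randomisation auxiliaries are selected, neither problem arises. No figure is offered for the loss from a post-randomisation covariate, since the documents do not show that one would be selected. This should be corrected, but it does not undermine the choice of analysis.

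**What to change.** 1. In SAP 6, replace the unconditional claim with: unbiased if outcomes are missing at random given the variables in a correctly specified model.
2. Limit auxiliary covariates in the treatment-effect models to variables measured before randomisation. Use any post-randomisation correlate of dropout only in an imputation-based sensitivity analysis.
3. Add one not-at-random sensitivity analysis for the primary PSS treatment contrast, for example a delta adjustment of imputed Happify-arm scores in fixed steps, and report the step at which the conclusion changes.

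The cost is a few sentences in the SAP, one imputation run and one extra table. No new data are needed.

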5 ENDPOINTS AND COVARIATES

The primary criterion of interest will be perceived stress scores, self-reported at baseline, 4-week midpoint, 8-week post, and 12-week follow-up. The secondary criterion of interest will be brooding scores at the same time points. Additionally, three exploratory outcomes will be examined at the same time points: optimism, sleep disturbance, and loneliness. The effect of the Happify treatment will be examined for each outcome.

In each model, we will covary the effects of participant age, gender, and race. Gender will be coded into two binary variables (0 = man or other, 1 = woman; 0 = woman or man, 1 = other). Race will be coded into a single binary variable (0 = White, 1 = all other races). Given that individuals who identify as White comprise almost 75% of the sample, this coding scheme prevents saturating each model with a large number of dummy codes while still preserving much of the racial distribution of the sample.

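### Gender is an optional free-text item but a covariate in every model, with no code for a blank; any participant who skipped it could drop out of the primary analysis

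*SAP*

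**What the plan says.** Protocol section II.b (Study Measures) lists the demographic items asked at baseline only. Gender is the one marked optional: "Gender Question (optional): Participants will be asked" for it, and "they will be provided with a text box to type in their response". Section II.a requires the baseline assessment to be completed before randomisation, so a teenager can be randomised without having answered this item.

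Gender is nevertheless an adjustment variable throughout. The protocol's repeated-measures ANOVA (section II.e) was to be run "controlling for participant age and gender". SAP section 5 says: "In each model, we will covary the effects of participant age, gender, and race". It then defines two indicators: "0 = man or other, 1 = woman; 0 = woman or man, 1 = other". Neither definition mentions a blank.

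SAP section 6 names multiple imputation and full information maximum likelihood as the standard remedies for missing data, then explains that the multilevel model makes them unnecessary. REML is to deal with missing outcome values. For everything on the right-hand side of the model the SAP relies on one expectation, stated without a figure: "we do not anticipate any significant missing data in the predictors or covariates". SAP section 7.2 names lme4 in R as the software.

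**The concern.** A mixed model fitted by REML tolerates unequal numbers of outcome records per person. It has no such tolerance for a missing covariate: a row without a value for gender cannot enter the likelihood, and lme4 by default discards it. Gender is constant within a person, so all four visits go at once. A randomised participant with complete stress and brooding scores would then leave the primary analysis, and the four other outcome models, because an optional question was skipped.

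Three things are at stake. Some precision is lost. The primary model no longer covers all randomised participants with outcome data; SAP section 4, which carries the heading for analysis sets, lists eligibility criteria and a usage subgroup and does not define an all-randomised set that would prevent this. And the sample analysed depends on a software default or an unrecorded recode instead of a stated rule. A recode that tests only for woman and other, for example, would give an empty string zero on both indicators, which is the code for man.

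**Working it through.** **Inputs from the documents.** Target sample 800, 400 per condition (Protocol section III); four assessments per participant; gender optional and free text (Protocol II.b); gender in every model, no code for a blank (SAP 5); REML for missing outcomes, no imputation (SAP 6); lme4 (SAP 7.2). The blank rate is not given and is assumed below. The documents give no significance level, power, effect size or standard deviation, so the 800 cannot be reproduced and is taken as stated.

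**Step 1: does the named software drop the participant?** A dataset was simulated with 800 participants, four visits each and complete outcomes, with gender blank at random for about 5%. This gave 43 blanks.
- Rows available: 800 × 4 = 3200.
- Expected after deletion: 3200 − 43 × 4 = 3028 rows, and 800 − 43 = 757 participants.
- lme4's lmer, by REML with a random intercept and default settings, used 3028 rows and 757 participants. Every visit of every blank participant was lost.
- With blanks kept as their own category, all 3200 rows and 800 participants remain.
- In a parallel REML mixed-model fit to the same data, the standard error of a condition-by-time term was 0.132 with deletion and 0.128 with the extra category. That is one simulated dataset and serves only as an illustration.

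**Step 2: how large would the loss be?** For a blank rate b:
- participants lost = 800 × b
- standard error multiplier = 1 / √(1 − b)

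| Assumed b | Lost of 800 | Multiplier | Rise in SE |
|---|---|---|---|
| 1% | 8 | 1/√0.99 = 1.005 | 0.5% |
| 2% | 16 | 1/√0.98 = 1.010 | 1.0% |
| 3% | 24 | 1/√0.97 = 1.015 | 1.5% |
| 5% | 40 | 1/√0.95 = 1.026 | 2.6% |

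**Step 3: what does that mean for power?** For scale only, assume a two-sided 5% level and a simple comparison of two means. With 400 per arm, 80% power corresponds to a standardised difference of (1.960 + 0.842) × √(2/400) = 0.198. Holding that difference fixed, power is 79.6% at 1% blank, 79.2% at 2% and 78.0% at 5%.

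**Step 4: can it bias the treatment contrast?** Gender is asked at baseline only, and the baseline assessment comes before assignment. Whether it is blank therefore cannot be affected by the arm. Deleting people on a pre-randomisation characteristic leaves the arms comparable in expectation. What changes is who the estimate represents (those who answered the item) and how precise it is.

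**The case against.** The strongest reply is that the SAP nowhere says that participants with a blank are removed, and nothing in the documents shows that there were any. That is right: the loss is an inference from lme4's default and the absence of a rule, and it holds only if blanks exist and are carried as missing values. A reader might infer that participants were in fact dropped; the documents do not support that.

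Timing also favours the authors. SAP section 2 dates the assessment data pull to March/April 2022 and the usage data pull to July 2022, and SAP section 5 already describes the racial make-up of the sample. The sentence about covariates may rest on a look at the data, and the number may be small. The SAP does not say so, and if the data were in hand the blanks could have been counted.

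The SAP does more about missing data than rely on unbalanced outcome rows. Section 6 plans missingness codes, tests of what predicts missingness, and auxiliary covariates; section 7.1 plans frequencies of the demographic covariates, which would reveal blanks. These would show the problem, but none assigns a value to a blank, so none prevents the deletion.

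Three stronger readings should be resisted. First, a biased treatment effect: blanks precede randomisation, so this does not follow. Second, that any odd typed answer is lost: the 'other' code can naturally take text that is neither man nor woman, so the gap is clear only for true blanks. Third, that race has the same fault: the protocol does not mark the race item as optional.

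**Conclusion.** The point holds in conditional form. The plan's expectation of complete covariates conflicts with its own optional item, and a blank passed to lme4 as missing would remove that participant from every outcome model. At assumed blank rates of 1% to 5% the loss is 8 to 40 of 800 and standard errors rise by about 0.5% to 2.6%; at 1% to 2% the power loss is below one percentage point under the assumptions in the working. These rates are illustrations, since no document supports any particular value. The consequence is lower precision and a primary analysis that omits some randomised participants with outcome data, without a declared rule. It is not confounding of the treatment comparison. This is a minor point, worth making because the repair is nearly free.

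**What to change.** In SAP section 5, code a blank gender entry as its own 'not reported' level, and state that typed answers that are neither man nor woman go to 'other'. In SAP section 6, replace the expectation about covariates with a statement that no randomised participant with outcome data is removed for a missing baseline covariate. Report the number of blanks by arm.

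Blanks should not be merged with 'other', because that mixes non-response with a gender category. A separate level is safe for the treatment comparison because the covariate is fixed before randomisation.

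The cost is one or two sentences, a recode and at most one extra parameter per model. If blanks are very few that parameter may be poorly estimated. If there are none, the level is empty and the model is unchanged.
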